### 2.2.2. Study Design Diagram

**Figure 1: Study Design Schematic**

EOS = End of study; OCA=obeticholic acid

▲ Biopsy (Subjects without a liver biopsy performed within 6 months before Day 1 will have a biopsy at the second Screening Visit).

\* Number of hepatic clinical outcomes adjudicated events accrued in placebo and OCA 25 mg groups combined with one Interim Analysis at 66% of information fraction.

### 2.2.3. Randomization Methodology

This study will be conducted in a double-blind, placebo-controlled manner. Subjects will be randomized 1:1:1 to placebo, OCA 10 mg, or OCA 25 mg. Randomization will be stratified by presence of diabetes at enrollment [yes/no] and use of TZDs or vitamin E at baseline [yes/no].

The randomization will be based on a predefined randomization code (generated by the Sponsor or designee) using an interactive web response system (IWRS), which the Sponsor intends will serve as a computer-based subject registration system at Screening and Day 1. The IWRS will serve as an investigational product inventory and management system and may be integrated with the study database.

The Investigator or designee will be required to register the subject in the IWRS and may be prompted to provide subject data necessary to properly randomize and allocate the subject to treatment. A randomization number will be assigned and investigational product dispensing information (ie, bottle number[s]) will be provided.

#### **2.2.4. Monitoring Guidelines and Unblinding**

Once enrolled, subjects will be monitored closely by reviewing their AEs, signs and symptoms, and laboratory values especially for potential hepatic injury and/or decompensation, pruritus, gallstone disease, symptomatic cholelithiasis and/or cholecystitis or pancreatitis, renal impairment and nephrolithiasis. Dosages for investigational product should be maintained consistent with the protocol during for the duration of the study. Any dose adjustments, interruptions, discontinuation, and any rechallenge of investigational product should be implemented per the criteria outlined in the protocol based on safety or tolerability concerns (see [Appendix D](#)).

Subjects that discontinue investigational product are expected to continue in the study until study termination, and the study will only terminate at the time when the required number of adjudicated events has accrued ([Section 3](#)).

Subjects who discontinue investigational product are expected to continue in the study and complete all scheduled study visits and assessments and are to be followed for the occurrence of outcome (hepatic) events.

The study will be conducted in a blinded manner with the exception a selected group of individuals who are unblinded for the Month 18 Interim Analysis as described in the DAP and Unblinding Plan. After the End of Study database lock, the study data will be completely unblinded.

### **2.3. Study Endpoints**

#### **2.3.1. Efficacy Analysis at Month 18 Interim Analysis**

##### **2.3.1.1. Primary Efficacy Endpoints**

The primary efficacy analysis for the Month 18 Interim Analysis will compare subjects treated with OCA (10 mg and 25 mg) versus placebo on histological improvement of nonalcoholic steatohepatitis (NASH) by assessing both of the following using NASH Clinical Research Network (CRN) scoring criteria:

- The percentage of subjects with improvement of fibrosis by 1 stage or more, no worsening of hepatocellular ballooning, no worsening of lobular inflammation, and no worsening of steatosis

- The percentage of subjects with resolution of NASH and no worsening of fibrosis

The study will meet its primary objective if either of the above primary endpoints is met.

### **2.3.1.2. Secondary Efficacy Endpoints**

#### **2.3.1.2.1. Histological Analysis:**

[figure not shown]
The analysis of the secondary histological efficacy endpoints for the Month 18 Interim Analysis, including the key secondary endpoint will compare subjects treated with OCA (10 mg and 25 mg) versus placebo on histological improvement by assessing the following using NASH CRN scoring criteria:

#### Key Secondary Endpoint:

- Percentage of subjects with improvement of fibrosis by at least 1 stage AND/OR resolution of NASH, without worsening of either

#### Secondary Endpoints:

- Percentage of subjects with no worsening of fibrosis AND no worsening of NASH
- Percentage of subjects with progression to cirrhosis
- Percentage of subjects with improvement of fibrosis by at least 2 stages
- Percentage of subjects with improvement of each key histological feature of NASH by at least 1 point (steatosis, lobular inflammation, and hepatocellular ballooning)
- Percentage of subjects with improvement of NAS by at least 2 points with no worsening of fibrosis
- Percentage of subjects with improvement of fibrosis and resolution of NASH as a composite endpoint and as defined by both endpoints being met in the same subject
- Percentage of subjects with resolution of fibrosis

## **2.3.2. Efficacy Analysis at End of Study**

### **2.3.2.1. End of Study Primary Estimands and Efficacy Endpoints**

The primary estimands at the end of study (EOS) will be the difference in time from randomization to the first occurrence of one of the post-randomization events listed below (clinical outcome composite endpoints). This will be assessed between OCA and placebo in adult subjects with (NASH) at fibrosis stage 2 or 3.

- Death (all-cause)
- MELD score  $\geq 15$
- Liver transplant
- Hospitalization (as defined by a stay of 24 hours or greater) for onset of:
  - Variceal bleed
  - Hepatic encephalopathy (as defined by a West Haven score of  $\geq 2$ )

- Spontaneous bacterial peritonitis (confirmed by diagnostic paracentesis)
- Ascites secondary to cirrhosis and requiring medical intervention (eg, diuretics or paracentesis)
- Histological progression to cirrhosis

For subjects who had an intercurrent event like investigational product interruption or dose adjustment or investigational product discontinuation and continued in the study, the events after those intercurrent events will still be evaluated for the analysis following Treatment Policy. If an intercurrent event like study discontinuation due to various reasons, withdrawal from study, or lost-to-follow-up occurred, the last available assessment prior to the intercurrent events will be used for the analysis following the While on Treatment Policy.

**Table 1: Estimands for Clinical Composite Outcome**

Estimands	Population	Endpoint	Intercurrent Events	Strategy for IEs	Population-Level Summary
Primary	ITT	Time to the first occurrence of the specific clinical composite outcomes	Investigational Product discontinuation or interruption or dose adjustment	Treatment Policy	Difference in time to the first occurrence of the clinical outcome events between OCA and placebo at end of study
	Same as above	Same as above	Study discontinuation due to various reasons or death, or withdrawal or lost to follow up	While on treatment policy	Difference in time to first occurrence of the events including death, and clinical outcomes before study discontinuation, withdrawal or lost to follow. Otherwise, it will be censored.

IE=intercurrent events; ITT=intent-to-treat; OCA=obeticholic acid

[figure not shown]
[figure not shown]
### 2.3.2.2. Secondary Efficacy Endpoints

#### 2.3.2.2.1. Histological Analysis

The analysis of the histological efficacy endpoints at End of Study will be based on the following endpoints analyzed for all post-baseline biopsies.

- Percentage of subjects with Improvement of fibrosis by at least 1 stage with no worsening of NASH
- Percentage of subjects with Resolution of NASH with no worsening of fibrosis

- Percentage of subjects with improvement of fibrosis by at least 1 stage AND/OR resolution of NASH, without worsening of either
- Percentage of subjects with no worsening of fibrosis AND no worsening of NASH
- Percentage of subjects with histological progression to cirrhosis
- Percentage of subjects with improvement of fibrosis by at least 2 stages
- Percentage of subjects with improvement of each key histological feature of NASH by at least 1 point (steatosis, lobular inflammation, and hepatocellular ballooning)
- Percentage of subjects with improvement of NAS by at least 2 points with no worsening of fibrosis
- Percentage of subjects with improvement of fibrosis and resolution of NASH as a composite endpoint and as defined by both endpoints being met in the same subject
- Percentage of subjects with resolution of fibrosis

[figure not shown]

[figure not shown]
## 2.4. Safety Evaluations at Month 18 and End of Study

Safety-related evaluations include:

- Vital signs
- 12-lead electrocardiograms (including central reading ECGs)
- Clinical laboratory evaluations, including
  - Hematology
  - Serum chemistry
  - Urinalysis
- Lipoprotein concentrations and [REDACTED]
- TEAEs including AESIs, including pruritus, hepatic disorders, renal disorders (including acute kidney injury), pancreatitis, gallbladder diseases and related complications, dyslipidemia, hyperglycaemia/new onset diabetes, and urolithiases, and cardiovascular events
- Adjudicated cardiovascular events
- Adjudicated hepatic safety events
- Adjudicated acute kidney injury events

### 3.4. Analysis Populations

Analysis populations for the Month 18 Interim Analysis and the End of Study Analysis are summarized in [Table 3](#).

#### 3.4.1. Month 18 Interim Analysis Populations

The Month 18 Interim Analysis data cutoff date (DCO) has been pre-specified to include all subjects' data for visits (scheduled or unscheduled) occurring on or before that date. The Interim Analysis Cohort (original Month 18 IA Cohort) will include all randomized subjects who received at least one dose of investigational product by the DCO. The original Month 18 IA Cohort will include all fibrosis stages (stages 1, 2 and 3).

The following analysis populations will be evaluated and used for presentation and analysis of Month 18 Interim Analysis data:

- The Safety Population will include the entire IA Cohort, all fibrosis stages (stages 1, 2 and 3), who received at least 1 dose of investigational product (OCA or placebo) by the DCO. Treatment assignment will be based on the treatment actually received.
- The Full Efficacy Analysis Population will include all original Month 18 IA Cohort subjects, randomized by 15 July 2017, including all fibrosis stages (stages 1, 2, and 3), who received at least 1 dose of investigational product. The selected randomization cut-off date ensures an adequate sample size for the efficacy assessment, considering that subjects randomized by 15 July 2017 would have reached their Month 18 biopsy visit by December 2018 based on 72 week treatment period. Treatment assignment will be based on the randomized treatment.
- The Intent-to-Treat (ITT) Population will include a subset of the Full Efficacy Analysis Population, limited to those subjects with fibrosis stage 2 or stage 3. Treatment assignment will be based on the randomized treatment. The ITT Population will be the primary efficacy analysis population.
- The modified ITT (mITT) Population will include all subjects from the ITT Population, with the exception of a subgroup of subjects who discontinued treatment (before the Month 18 Visit and without an end of treatment biopsy) between 13 Sep 2017 and 19 Dec 2017 for the following reasons: withdrawal of consent, lost to follow-up, and due to other reasons. The observed increase in the number of discontinuations during the above-mentioned period was an unintended consequence of 1) safety communications eliciting concern from subjects and physicians and 2) increased subject and site burden due to the safety amendment. Treatment assignment will be based on the randomized treatment. The mITT population will serve as a supportive analysis population.
- The Per Protocol (PP) Population will include all subjects from the ITT Population who completed at least 15 months of treatment, had a Month 18/ end of treatment biopsy, were on investigational product for at least 30 days immediately preceding the biopsy, and did not have any major protocol deviation ([Section 5.5](#)) that could

potentially affect the efficacy conclusions. Treatment assignment will be based on the randomized treatment.

- The PK Population will include all subjects who received OCA and have at least one confirmed fasted analyzable sample. Subjects must have been fasting for approximately 8 hours before the visit and must not have any major protocol deviations that potentially affect exposure levels. The PK Population will be used for OCA PK analysis.

### **3.4.2. End of Study Analysis Populations**

- The Safety Population will include all randomized subjects who received at least 1 dose of investigational product (OCA or placebo). Treatment assignment will be based on the treatment actually received.
- The Full Efficacy Analysis Population will include all randomized subjects, all fibrosis stages (stages 1, 2 and 3), who received at least 1 dose of investigational product. Treatment assignment will be based on the randomized treatment.
- The Intent-to-Treat (ITT) Population will be a subset of the Full Efficacy Analysis Population, limited to those subjects with fibrosis stage 2 or stage 3. Treatment assignment will be based on the randomized treatment. The ITT Population will be the primary efficacy analysis population. The Per Protocol (PP) Population will include all subjects from the ITT Population who did not have any major protocol deviation ([Section 5.5](#)) that could potentially affect the efficacy conclusions and at least 80% compliance with investigational product ([Section 10.1](#)). Treatment assignment will be based on the randomized treatment.
- The PK Population will include all subjects who received OCA and have at least one confirmed fasted analyzable sample. Subjects must have been fasting for approximately 8 hours before the visit and must not have any major protocol deviations that potentially affect exposure levels. The PK Population will be used for OCA PK.

**Table 3: Analysis Populations for the Month 18 Interim Analysis and End of Study Analysis**

Population	Fibrosis Stage	Description	
		Month 18 Interim Analysis	End of Study
Safety	1,2 and 3	Randomized subjects who received at least one dose of investigational product by the DCO (IA Cohort)	Randomized subjects who received at least one dose of investigational product.
Full Efficacy Analysis	1,2 and 3	All subjects, randomized by 15 July 2017, all fibrosis stages (stages 1, 2 and 3), who received at least 1 dose of investigational product.	Randomized subjects who received at least one dose of investigational product.
ITT	2 and 3	Subset of Full Efficacy Analysis Population	Subset of Full Efficacy Analysis Population
mITT	2 and 3	Subset of ITT Population which excludes treatment discontinuation (before the Month 18 Visit and without an end of treatment biopsy) between 13 Sep 2017 to 19 Dec 2017 due to withdrawal of consent, lost to follow up and other reasons	Not applicable
Per Protocol	2 and 3	Subset of ITT Population who completed at least 15 months of treatment, had a Month 18/end of treatment biopsy, were on investigational product for at least 30 days just preceding the biopsy, and did not have any major protocol deviation	Subset of ITT Population with no major protocol deviation and at least 80% compliance with investigational product ( Section 10.1 )

#### 4. GENERAL STATISTICAL METHODS

Individual subject data obtained from electronic case report forms (eCRFs), local laboratories, central laboratories, external sources, and any derived data will be presented in data listings by subject. All data listings that contain an evaluation date will contain a relative study day. Pre-treatment and on-treatment study days are numbered relative to the day of the first dose of investigational product which is designated as Day 1. The preceding day is Day -1, the day before that is Day -2, etc.

For categorical variables, summary tabulations of the number and percentage of subjects within each category (with a category for missing data) of the parameter will be presented. Percentage calculations will be based on non-missing data unless otherwise specified.

In response analysis [yes/no] of histological endpoints, the comparison between treatment groups will be performed using CMH test stratified by the randomization strata (type 2 diabetes at enrollment [yes/no] and use of TZDs/glitazones or vitamin E at baseline [yes/no]).

For continuous variables, the number of subjects, mean, standard deviation (SD), standard error of the mean (SEM), median, 25th and 75th quartiles, minimum, and maximum values will be presented.

Longitudinal summaries of continuous variables will present absolute values, change, and percentage change from baseline at each post-baseline visit.

For continuous endpoints satisfying normality assumptions, change from baseline and percentage change from baseline over time will be analyzed using mixed-effect repeated measures (MMRM) model with treatment, baseline, visit, visit by treatment interaction and stratification factors to be included in the model. An unstructured covariance model will be used. If the computational algorithm fails to converge, an appropriate covariance structure will be selected. Estimates of least-square (LS) means, standard errors will be presented by treatment group. Unless indicated otherwise 95% CIs will be provided for efficacy endpoints by treatment group.

Time-to-event data will be summarized using Kaplan-Meier (KM) methodology using 25th, 50th (median), and 75th percentiles with associated 2-sided 95% CIs, as well as the percentage of censored observations. KM estimates will be plotted as a “survival curve” for each treatment group, with the number at risk identified. In addition, time-to-event data will be summarized with descriptive statistics for those subjects with an event. Subjects who do not experience an event will be censored. Subjects who do not experience an event will be censored at the date of last contact for clinical outcome endpoints and will be censored at the earliest date of last dose date+30 days, end of study, death date or date cut-off date for treatment-emergent adverse events (TEAEs). The censor date for time to resolution events will be the earliest date of end of study, death date or date cut-off date.

#### **4.1. Computing Environment**

All descriptive statistical analyses will be performed using SAS statistical software Version 9.4 or higher unless otherwise noted. Medical history and AEs will be coded using Medical Dictionary for Regulatory Activities (MedDRA). Concomitant medications will be coded using World Health Organization (WHO) Drug Dictionary.

#### **4.2. Baseline Definitions**

The baseline value for statistical analyses of quantitative parameters (except lipoprotein evaluations and markers of glucose metabolism) is defined as the mean of all available evaluations, at the individual subject level, prior to the first administration of investigational product, unless otherwise specified. If there is only one evaluation prior to the first administration of investigational product, then the available data from this evaluation will be used as the baseline value. Quantitative parameters include, but are not limited to, lab parameters (except lipoprotein evaluations and markers of glucose metabolism), electrocardiogram measures, exploratory biomarkers, pharmacodynamic parameters, and vital signs.

The baseline value for analyses of lipid parameters and markers of glucose metabolism is defined as the last fasted evaluation prior to the first administration of investigational product, unless otherwise specified.

The baseline value for analyses of qualitative parameters (eg, normal/abnormal), cardiovascular risk assessments, and patient-reported outcomes is defined as the last evaluation prior to the first administration of investigational product. Baseline definition of each assessment is provided in [Appendix A](#).

### 4.3. Visit Windows

[figure not shown]
Visit windows will be defined around the target date of the visit as planned in the protocol. Day 1 is the first day of receiving investigational product (OCA or placebo). Month 18 (Week 72) biopsy window is Week 60 to Week 96. For all assessments, other than biopsy, each visit window will have the target date as the center and the lower bound is the midway between the target date of this window and the preceding one. The upper bound is the midway between the target date of the current window and the following one. If more than one assessment is collected within a window, then the assessment closest to the target date will be selected. If more than one assessment with the same distance from the target date, then the last assessment will be used. “Last” will be based on sorting by date, time, record number/sequence number. [Appendix B](#) shows the visit windows of each visit up to Month 78.

### 4.4. Examination of Subgroups

There will be 3 types of analyses:

1. Subgroup analyses for the primary and key secondary efficacy endpoint using the ITT, mITT, and PP Populations will include the following factors:
  - a. Baseline diabetes status: Yes, No
  - b. BMI (  $< 30 \text{ kg/m}^2$ ,  $\geq 30 \text{ kg/m}^2$  and  $< 35 \text{ kg/m}^2$ ,  $\geq 35 \text{ kg/m}^2$  )
  - c. Baseline Vitamin E or TZD use: Yes, No
  - d. Age categories:  $<65$ ,  $\geq 65$  years and  $<75$ ,  $\geq 75$  years
  - e. Gender: Male, Female
  - f. Race: White, Non-White (Black or African American, Asian, Native Hawaiian or Other Pacific Islander, American Indian or Alaska Native)
  - g. Geographic Region: North America, Europe, and the Rest of the World (ROW); including Asia as a subgroup
  - h. Baseline Fibrosis Score: F1, F2 and F3
  - i. Baseline NAS: ( $<6$ ,  $\geq 6$ ) (Only for the NASH primary efficacy endpoint)
  - j. Baseline and concomitant statin medication use (no concomitant use, prior and concomitant use, new concomitant use)
  - k. Baseline and concomitant use of anti-diabetic medications (no concomitant use, prior and concomitant use, new concomitant use)

2. Subgroup analyses for safety (selected safety endpoints) will be generated using the Safety Population and will include the following factors:
  - a. Baseline diabetes status; Yes, No
  - b. Baseline Fibrosis Score: F1, F2 and F3
  - c. Age categories: <65, ≥65 years, ≥75 years
  - d. Gender: Male, Female
  - e. Baseline in BMI (< 30 kg/m^2, ≥ 30 kg/m^2 and < 35 kg/m^2, ≥ 35 kg/m^2 )
  - f. Baseline cardiovascular medical history: Yes, No
  - g. Baseline Framingham (FRS) risk score: ≤10, >10 - ≤20, >20
  - h. Baseline eGFR
  - i. Baseline and concomitant statin medication use (no concomitant use, prior and concomitant use, new concomitant use)
  - j. Baseline and concomitant medication use of antidiabetic medication (no concomitant use, prior and concomitant use, new concomitant use)
  - k. Baseline and concomitant medication use of antihypertensive medication (no concomitant use, prior and concomitant use, new concomitant use)
  - l. Quartiles of the mean HDL values after first dose of investigational product for adjudicated cardiovascular event
  - m. Quartiles of the mean LDL values after first dose of investigational product for adjudicated cardiovascular event
  - n. Baseline gallbladder (ultrasound): Cholecystitis (yes vs no)
3. The change from baseline in the following parameters will be analyzed by response to the primary endpoints and treatment group. These summaries will be based on subjects with Month 18 biopsy.
  - a. Liver biochemistry: ALT, AST, ALP, and GGT
  - b. Lipids: LDL, HDL, VLDL and total cholesterol

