16.8. Examination of Subgroups

Both at the interim and final analyses, the primary and key secondary efficacy endpoints will be analyzed for subject subgroups (eg, age, sex, and race) using the ITT population. Subgroups will be assessed at Baseline and only if there are a sufficient number of subjects in each group (eg, >5 subjects per group).

Key subgroups of interest are fibrosis stage and diabetes status. Additional parameters for subgroup analyses include, but are not limited to: age, sex, race, BMI, NAS, ballooning, FRS, statin or antihypertensive medication use, ALT, AST, GGT, and geographic region. Further details regarding subgroups analyses will be specified in the SAP.

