## **10.2. Prior and New Concomitant Medications**

Verbatim terms on eCRFs will be mapped to Anatomical Therapeutic Chemical (ATC) class and Preferred Name using the WHO Drug Dictionary Enhanced.

Pretreatment concomitant medications are those medications with start and stop prior to the initial dose of investigational product also classified as no concomitant medication. Prior concomitant medications are those medications started prior to and continued after the initial dose of investigational product. New concomitant medications are those medications that were started after the initial dose of investigational product. If it cannot be determined whether the medication was a new concomitant medication due to a partial start or stop date or if the medication is taken on the same date as the initial dose of investigational product, then it will be counted as a new concomitant medication.

No concomitant, prior, and new concomitant medications will be summarized separately for each treatment group by WHO ATC level 2, WHO ATC level 4, and preferred name using the Safety Population. These summaries will present the number and percentage of subjects using each medication. Subjects may have more than one medication per ATC level and preferred name. At each level of subject summarization, a subject is counted once if he/she reported one or more medications at that level. Each summary will be ordered by descending order of incidence of ATC level and preferred name within each ATC level.

Extent of exposure of newly initiated use (after the 1st dose) of vitamin E, thiazolidinediones, bile acid sequestrants (BABR), statins and other lipid-lowering medications, will be calculated as follows:

$$\text{Exposure to the concomitant medication} = \{[(\text{Date of last dose} - \text{Date of 1}^{\text{st}} \text{ dose}) + 1] - \text{Total duration of temporary interruptions}\}$$

Missing start and end dates will be imputed as described in [Appendix A](#). Extent of exposure will be summarized by treatment group as described in the General Statistical Methods ([Section 4](#)).

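### Efficacy subgroups by statin and antidiabetic use (SAP 4.4, items 1j and 1k) depend on drugs started after first dose, whereas the protocol fixes efficacy subgroups at baseline

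*SAP*

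**What the plan says.** Protocol 16.8 covers efficacy subgroups at every analysis: "Both at the interim and final analyses, the primary and key secondary efficacy endpoints will be analyzed for subject subgroups". It then sets the rule: "Subgroups will be assessed at Baseline and only if there are a sufficient number of subjects in each group". Its list of further factors, which is expressly not exhaustive, includes "age, sex, race, BMI, NAS, ballooning, FRS, statin or antihypertensive medication use". Antidiabetic use is not named, and further detail is left to the SAP.

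SAP 4.4 lists the efficacy subgroup factors. Item 1j is "Baseline and concomitant statin medication use (no concomitant use, prior and concomitant use, new concomitant use"). Item 1k is "Baseline and concomitant use of anti-diabetic medications (no concomitant use, prior and concomitant use, new concomitant use"). Item 1c, in the same list, is fixed at baseline: "Baseline Vitamin E or TZD use: Yes, No".

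SAP 10.2 supplies the definitions: "New concomitant medications are those medications that were started after the initial dose of investigational product", with no upper time limit, and "Prior concomitant medications are those medications started prior to and continued after the initial dose of investigational product". It also counts as new any drug started on the day of first dose, and any drug whose status cannot be settled because a date is partial.

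Safety items 2i-2k in SAP 4.4 reuse the three levels. Items 2l-2m use quartiles of mean HDL and LDL after first dose, for adjudicated cardiovascular events. SAP 10.4.3 applies the three-level statin variable under a label that calls it use at baseline.

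**The concern.** A subgroup contrast is protected by randomisation only if membership is fixed before treatment can act on it. Here two of the three levels are not. A subject who was not taking a statin at first dose ends up in *new use* or *no use* according to what happens during follow-up.

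The protocol gives reasons to expect treatment to influence that:
- Section 5.3 reports an LDL rise of about 20-25% at Week 4 on OCA, before statins were added, and says of another study that the lipid change attenuated with continued treatment.
- Section 5.5 reports raised LDL, lowered HDL and a modest, transient rise in glycaemic measures.
- Appendix A makes a confirmed LDL rise of 15% or more the starting point for a risk assessment that can end in a statin start.

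OCA and placebo subjects within *new use*, and within *no use*, may therefore differ in prognosis. For a time-to-event endpoint there is a second problem. A subject must remain event-free long enough to start the drug, so the classification itself uses survival time. If the arms differ in how many subjects start, or how early, the two effects do not cancel.

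What is at stake is the reading of the subgroup tables: a contrast in these levels could show an effect that is not there or hide one that is.

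**Working it through.** **Step 1: the texts side by side.** Protocol 16.8 assesses efficacy subgroups at baseline and names statin use. Item 1j applies to the primary and key secondary efficacy endpoint and has a level that SAP 10.2 defines by starts after first dose. These do not agree. Item 1k has the same structure, but its factor is not named in 16.8. The key changes and rationales in SAP 11 do not mention either item.

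**Step 2: which levels are affected.** *New use* is post-dose by definition. *No use* is affected because it means not having started later. *Prior and concomitant use* is in effect a baseline level, but only if subjects who switch or add an agent stay in it. SAP 10.2 classifies medications, not subjects, and gives no rule for a subject with both a prior and a new drug.

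**Step 3: illustration under a true null.** The plan has no figure to reproduce, and it gives no start rates by arm. All inputs below are assumptions.
- Event hazard λ = 0.03-0.05 per year, the same in both arms. Rough check: 288 events (SAP 2.2.1) in two thirds of 2085 subjects (1390), over an assumed mean of 4 to 7 years: 288/(1390×4) = 0.052 and 288/(1390×7) = 0.030. The 2085 is the original design figure. If all 110 extra subjects (2480 - 2370) were stage 2-3, the base is two thirds of 2195 (1463) and the range is 0.049 to 0.028.
- Placebo starts: 0.05 per year.
- Only starts before the event or the end of follow-up T count.

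Let S(t) be the probability of not having started by time t. In *new use*:

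events = ∫₀ᵀ λe^(-λt)(1-S(t)) dt

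person-time = ∫₀ᵀ tλe^(-λt)(1-S(t)) dt + T e^(-λT)(1-S(T))

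For *no use*, replace 1-S by S. The false ratio is the OCA rate over the placebo rate within the level.

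Worked case, λ = 0.04, T = 6:

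| Start rate per year | New-use event rate | No-use event rate |
|---|---|---|
| Placebo, 0.05 | 0.02098 | 0.04633 |
| OCA, 0.30 in year 1, then 0.05 | 0.02926 | 0.04763 |
| OCA, 0.30 throughout | 0.02555 | 0.10344 |

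Year 1 only: 0.02926/0.02098 = 1.39 (*new*) and 0.04763/0.04633 = 1.03 (*no*). Throughout: 0.02555/0.02098 = 1.22 and 0.10344/0.04633 = 2.23. Merging the two levels gives 0.04/0.04 = 1.00 in both cases.

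Over the full ranges:

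| OCA start pattern | New use | No use |
|---|---|---|
| Equal to placebo | 1.00 | 1.00 |
| 0.10-0.50 in year 1 only, T = 4-6 years | 1.13-1.54 | 1.01-1.08 |
| 0.10-0.30 throughout, T = 4-8 years | 1.03-1.27 | 1.11-2.98 |

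**Step 4: direction.** Subjects stay on the visit schedule after a non-fatal event (SAP 2.2.1), so later starts can be recorded, and the SAP does not say whether they count. Take the year-1-only pattern, count such starts, and let the event itself prompt a start in 25-80% of remaining non-users, with 10% or 30% of first events fatal. The *new use* ratio then falls below 1: 0.86-0.96 at 0.10 per year and 0.48-0.84 at 0.50. The sign is therefore not determined either.

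**The case against.** **End of Study is not stated.** A reader might infer that the End of Study composite will certainly be analysed this way. The SAP does not say so. Item 1 of 4.4 is worded for Month 18: it uses the mITT population, which Table 3 marks as not applicable at End of Study; it refers to a key secondary endpoint that the SAP names only at Month 18; and item 1i mentions the NASH primary endpoint. This objection stands as a limit. Against it, protocol 16.8 requires subgroups at the final analysis, SAP 1 says this version's updates concern End of Study, and SAP 4.4 has no other efficacy list.

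**Antidiabetics are not named.** Item 1k is not as plain a conflict as 1j. That stands. The methodological argument applies to it all the same.

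**Safety items.** A reader might extend the charge of conflict to 2i-2m. The rule in 16.8 is written for efficacy endpoints, SAP 10 makes safety comparisons descriptive unless otherwise specified, and SAP 10.4.9.1 can be read as describing only subjects with events. SAP 10.4.9.2 already plans baseline LDL and HDL quartiles for serious cardiovascular events. No conflict is shown there.

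**The figures are fragile.** They are crude rate ratios, whereas the planned analysis is a stratified log-rank test and Cox model, and the *no use* result depends heavily on how long a raised start rate lasts. That stands too: they show that the bias can be material, not how large it will be.

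**Conclusion.** The point holds for the efficacy items: clearly for 1j, where the SAP departs from the protocol's baseline rule on a factor the protocol names, and by the same logic for 1k. Contrasts in the new-use and no-use levels are not protected by randomisation, and on a time-to-event endpoint they carry immortal-time bias.

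The consequence is confined to interpretation of subgroup tables. The primary comparison and its alpha are untouched, because these subgroups lie outside the testing scheme in SAP 6.3. Month 18 is complete. The open exposure is the End of Study composite, conditional on the 4.4 list being carried over. The documents do not allow the size or direction to be estimated; the illustrative ratios rest on assumed start rates and vanish if the arms start these drugs equally.

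**What to change.** In SAP 4.4, define 1j and 1k by use at first dose (yes/no), as item 1c does, and state that the list applies at End of Study. Two rules need to go with it:
- Subjects who later switch or add an agent stay in their baseline level.
- Drugs started on the day of first dose, and drugs with partial dates, are classed by a stated rule. At present SAP 10.2 counts them as new.

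Show drug starts after first dose only as by-arm descriptive summaries; SAP 10.2 already provides most of this.

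Minor: correct the at-baseline label in SAP 10.4.3, since the variable includes new use. For safety items 2i-2m, add only a note that levels based on post-dose drug use or post-dose lipids are not for between-arm comparison.

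The cost is SAP wording and programming. Baseline medication use is already collected and summarised (SAP 5.2); no new data or tests are needed. The change should be made before End of Study unblinding.
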